2. TRIAL OBJECTIVES AND ENDPOINTS

2.1 MAIN OBJECTIVES, PRIMARY AND SECONDARY ENDPOINTS

2.1.1 Main objectives

The overall purpose of this extension trial is to assess long-term safety, tolerability, and efficacy of BI 730357 in patients with moderate to severe chronic plaque psoriasis.

2.1.2 Primary endpoint

- The occurance of treatment emergent adverse events (TEAEs)
- up to Week 288.

2.1.3 Secondary endpoints

- Achievement of Psoriasis Area and Severity Index (PASI)50/PASI75/PASI90/ PASI100 at Week 24
- Achievement of Static Physician's Global Assessment (sPGA) clear or almost clear at Week 24
- Achievement of sPGA clear at Week 24
- Time to loss of PASI50/PASI75/PASI90/PASI100 for patients who achieve the response up to Week 288
- Time to loss of sPGA clear or almost clear for patients who achieve the response up to Week 288
- Time to loss of sPGA clear for patients who achieve the response up to Week 288

c22181693-04 Page 26 of 84

3. DESCRIPTION OF DESIGN AND TRIAL POPULATION

OVERALL TRIAL DESIGN AND PLAN 3.1

Trial 1407-0005 is a multicentre, long-term extension trial in patients who have completed Phase II PoC/dose-ranging trial 1407-0030 with demonstrated improvement in disease severity and acceptable safety and tolerability of trial drug, as described below. The trial is designed to evaluate long-term safety and efficacy of BI 730357 in patients with moderate-tosevere plaque PsO.

Two groups of patients are to be entered into this trial, including up to (approximately) 180 patients entered in the original trial 1407-0030 protocol (now Part 1) and up to (approximately) 90 patients entered in an extended dose-ranging segment, now Part 2 of the amended trial 1407-0030 protocol. Actual numbers of subjects entering the extension trial are to be determined by response in the preceding study and the number of patients that participate in the extension study.

In the first group (Part 1), patients will be considered eligible to participate in this long-term extension trial upon completing the trial 1407-0030 Week 24 end-of-treatment visit with a \geq PASI50 response. BI 730357 dose levels of up to 200 mg *q.d.* are to be administered under fasting conditions to patients in this group, reflecting the dose levels evaluated during Part 1 of trial 1407-0030.

- Patients entering the extension trial will remain on their blinded BI 730357 dose treatment from the preceding trial until the open label period of 1407-0005 begins at Visit 2/Week 12.
- At Visit 2/Week 12, patients presently assigned to double blind treatment of placebo, 25 mg, 50 mg, and 100 mg will be reassigned to the 100 mg open label dose, and patients presently assigned to the double blind treatment of 200 mg will be reassigned to 200 mg open label dose. Refer to Figure 3.1: 1.

In the second patient group (Part 2), patients will be considered eligible to participate in this trial upon completing the trial 1407-0030 Week 12 end-of-treatment visit with a ≥PASI50 response or perceived patient improvement, at the discretion of the Investigator. Patients are to be considered eligible only if also without ongoing AEs consistent with intolerance of trial medication (including gastric intolerance) that in the opinion of the investigator would compromise the safety of the patient.

All patients entering the extension trial are to be assigned at Visit 1 to receive openlabel treatment with 400 mg q.d. (fed), the anticipated therapeutic BI 730357 dose. Refer to Figure 3.1: 2.

It is expected that Visit 1 of trial 1407-0005 will be performed on the same day of the EOT Visit of trial 1407-0030 in both patient groups. In the event that patients completing Part 2 of trial 1407-0030 are not able to be entered immediately into the extension trial due to administrative reasons (e.g., pending protocol approval, availability of trial medication), Visit 1 of the extension trial may be delayed for no more than 16 weeks. In the event of a delay, the CTM should be consulted and refer to the Flow Chart for procedures to be conducted.

The treatment period is this trial will be approximately 6 years.

[figure not shown]

Figure 3.1: 1 Trial 1407-0005 dose assignment/reassignment for patients entering from Part 1 of trial 1407-0030

[figure not shown]

Figure 3.1: 2 Trial 1407-0005 dose assignment for patients entering from Part 2 and continuing from Part 1 of trial 1407-0030

Page 28 of 84

Clinical Trial Protocol

Dose selection at Week 12 is based on the safety and tolerability data from the SRD Trial 1407.1 and the MRD Trial 1407-0002, and will be contingent on DMC evaluation of all available data from Phase II trial 1407-0030. For patients entering from Part 1 of trial 1407-0030, if an unacceptable risk regarding the safety of the 200 mg dose level is reported by the DMC, the open label BI 730357 dose assignments beginning at Week 12, as shown in Figure 3.1: 1, is to be altered to assign all patients to the 100 mg *q.d.* dose group. For additional

details and logistics, refer to Section 8.7. Refer to Section 4.1.2 for dose selection rationale.

All patients entering from Part 2 of trial 1407-0030 are to receive the 400 mg q.d. dose, as long as no unacceptable risks are identified during Part 2 of trial 1407-0030. Once Part 2 patients begin enrolling in this trial, existing patients receiving 100 mg q.d. in this trial will be given the option to titrate up to the 200 mg q.d. dose, if the investigator determines that the patients may benefit from the higher dose.

3.2 DISCUSSION OF TRIAL DESIGN, INCLUDING THE CHOICE OF CONTROL GROUP(S)

Trial 1407-0005 is designed as a long-term extension clinical trial, and is expected to generate additional safety information to support registration submissions. Therefore, the primary endpoint is focused on safety. All patients who complete treatment with BI 730357 or placebo in the preceding Trial 1407-0030 and achieve a PASI50 response at Week 24 of that trial will be invited to participate to receive long-term treatment. Our goal in this study is to obtain additional safety, tolerability and efficacy data following long-term drug administration

For patients entering the extension trial from Part 1 of trial 1407-0030, the 12-week double blind treatment period (refer to Section 3.1) is intended to maintain the blind of the preceding trial while collecting additional data for the doses allocated at EOT in the preceding trial. After DMC review of all available safety data from 1407-0030 (refer to Section 8.7), the dose levels selected for the open label period of the extension trial will be confirmed and the long-term assessment of the 100 mg *q.d.* and 200 mg *q.d.* dose groups will begin at Visit 2/Week 12 (refer to Section 3.1). Visit 2.1 will be conducted by telephone 2 weeks after this transition as a precaution to monitor patient safety. Trial 1407-0005 may include placebo patients who have achieved a PASI 75 at Week 12 of 1407-0030 and a PASI50 at Week 24 of 1407-0030. Patients in this category that have meet these efficacy criteria would also need to be satisfied with their blinded treatment allocation at Week 24 of trial 1407-0030 and therefore selected to continue treatment by participating in the extension study. These patients will begin active treatment of 100 mg BI 730357 at Visit2/Week 12 of the extension study.

Based on safety and efficacy data from Part 1, Part 2 of trial 1407-0030 extends dose ranging of BI 730357 to 400 mg q.d. and 200 mg b.i.d., to be administered under fed conditions. Given that PoC efficacy has been demonstrated in Part 1 of trial 1407-0030, in the second patient group, patients are to be considered eligible to participate in 1407-0005 upon completing the trial 1407-0030 Week 12 end-of-treatment visit with \geq 50% improvement in PASI50 or perceived patient improvement, at the discretion of the Investigator. Furthermore, given that patients in this group are to receive long-term BI 730357 at a substantially higher dose than in those in the first group, in the interest of safety, patients are to be considered

Page 29 of 84

eligible only if also without ongoing AEs consistent with intolerance of trial medication (including gastric intolerance), that in the opinion of the investigator would compromise the safety of the patient.

. Visits 1.1, 1.2 and 1.3 will be conducted in person for these patients to monitor patient safety, particularly as placebo patients may continue into this trial and receive active drug.

As a trial with an open label period, we realize that no powered or controlled analysis can be done. However, we will be able to evaluate initial tendencies and at the same time permit our early study participants an opportunity to maintain access to a therapy that has the potential to have clinical benefit.

3.3 SELECTION OF TRIAL POPULATION

The trial is intended to provide extended access of BI 730357 to up to approximately 180 male and female patients in Part 1 and approximately 90 patients in Part 2 that complete Trial 1407-0030 at approximately 30 study sites.

A log of all patients enrolled into the trial (i.e. who have signed informed consent) will be maintained in the Investigator Site File (ISF) irrespective of whether they have been treated with investigational drug or not.

If a patient is enrolled in error (does not meet all inclusion criteria or meets one or more exclusion criteria on the day of enrolment), the sponsor should be contacted immediately.

3.3.1 Main diagnosis for trial entry

Patients with moderate-to-severe plaque psoriasis who have completed treatment in the preceding trial.

Please refer to Section 8.3.1 (Source Documents) for the documentation requirements pertaining to the in- and exclusion criteria.

3.3.2 Inclusion criteria

1. WOCBP¹ must be ready and able to use highly effective methods of birth control per ICH M3 (R2) that result in a low failure rate of less than 1% per year when used consistently and correctly from date of screening until 4 weeks after last treatment in this trial. A list of contraception methods meeting these criteria is provided in the patient information.

(¹ A woman is considered of childbearing potential (WOCBP), i.e. fertile, following menarche and until becoming post-menopausal unless permanently sterile.

Permanent sterilisation methods include hysterectomy, bilateral salpingectomy and bilateral oophorectomy. Tubal ligation is NOT a method of permanent sterilisation.

A postmenopausal state is defined as no menses for 12 months without an alternative medical cause.)

- 2. Patients with moderate-to-severe plaque PsO who have completed treatment in the preceding trial without early discontinuation, agree to continue treatment in 1407-0005, and
- for patients entering from Part 1 of trial 1407-0030

Page 30 of 84

- o achieve a ≥PASI50 response upon completing the trial 1407-0030 Week 24 end-of-treatment visit
- for patients entering from Part 2 of trial 1407-0030
 - o achieve a ≥PASI50 response upon completing the trial 1407-0030 Week 12 endof-treatment visit or perceived patient improvement, at the discretion of the Investigator
- 3. Signed and dated written informed consent in accordance with ICH-GCP and local legislation prior to admission to the trial.

3.3.3 Exclusion criteria

Having developed any of the following exclusion criteria from the preceding study:

- 1. Nonplaque forms of PsO (including guttate, erythrodermic, or pustular), current druginduced PsO (including a new onset or exacerbation of PsO from, e.g., beta blockers, calcium channel blockers, lithium), active ongoing inflammatory diseases (including but not limited to inflammatory bowel disease (IBD)) other than PsO that might confound trial evaluations.
- 2. Previous enrolment in this trial.
- 3. Currently enrolled in another investigational device or drug trial or is receiving other investigational treatment(s) (with the exception of 1407-0030).
- 4. Intake of any restricted medication as specified in Section 4.2.2.1 or any drug considered likely to interfere with the safe conduct of the trial.
- 5. Any plan to receive a live vaccination during the conduct of the trial.
- 6. Patients not expected to comply with the protocol requirements or not expected to complete the trial as scheduled.
- 7. Chronic alcohol or drug abuse or any condition that, in the investigator's opinion, makes the patient an unreliable trial participant or unlikely to complete the trial.
- 8. Women who are pregnant, nursing, or who plan to become pregnant while in the trial.
- 9. Any documented active or suspected malignancy, except appropriately treated basal cell carcinoma of the skin, squamous cell carcinoma of the skin, or *in situ* carcinoma of uterine cervix.
- 10. Relevant chronic or acute infections including human immunodeficiency virus (HIV), viral hepatitis, and tuberculosis.
- 11. Evidence of a disease (including known or suspected IBD, cardiovascular disease), or medical finding that in the opinion of the Investigator is clinically significant and would make the study participant unreliable to adhere to the protocol or to complete the trial, compromise the safety of the patient, or compromise the quality of the data.
- 12. Any suicidal ideation, including grade 4 or 5 in the Columbia Suicide Severity Rating Scale (C-SSRS) in the past 12 months (i.e., active suicidal thought with intent but without specific plan), or active suicidal thought with plan and intent in the past.

Page 31 of 84

- 13. Unwillingness to adhere to the rules of UV-light protection as described in Section 4.2.2.2.
- 14. Ongoing AEs consistent with intolerance of trial medication (including gastric intolerance) from 1407-0030, that in the opinion of the investigator would compromise the safety of the patient.

3.3.4 Withdrawal of patients from treatment or assessments

Patients may discontinue trial treatment or withdraw consent to trial participation as a whole ("withdrawal of consent") with very different implications; please see Sections 3.3.4.1 and 3.3.4.2 below.

Every effort should be made to keep the patients in the trial: if possible on treatment, or at least to undergo the procedures for early treatment discontinuation, follow up, and vital status collection.

Measures to control the withdrawal rate include careful patient selection, appropriate explanation of the trial requirements and procedures prior to trial enrolment, as well as the explanation of the consequences of withdrawal.

The decision to discontinue trial treatment or withdraw consent to trial participation and the reason must be documented in the patient files and case report form (CRF). If the reason for discontinuation is death, this should be reported on the SAE form as well, regardless of causal relationship.

3.3.4.1 Discontinuation of trial treatment

An individual patient may be withdrawn from trial treatment if:

- The patient wants to discontinue trial treatment, without the need to justify the decision.
- The patient has repeatedly shown to be non-compliant with important trial procedures and, in the opinion of both, the investigator and sponsor representative, is not willing or able to stick to the trial requirements in the future.
- The patient experiences an intolerable increase of PsO, the trial medication will be discontinued and anti-psoriatic agents may be used as rescue medications (refer to Section 4.2.1).
- The patient needs to take concomitant drugs that interfere with the investigational product as listed in Table 4.2.2.1: 1.
- The patient can no longer be treated with trial medication for other medical reasons (such as surgery, adverse events, other diseases, or pregnancy).
- The patient develops suicidal ideation of type 4 or 5 in the C-SSRS (i.e., active suicidal thought with intent but without specific plan, or active suicidal thought with plan and intent). The patient should immediately be referred to a mental health professional for further work-up.
- In addition to these criteria, the physician may discontinue subjects at any time based on his or her clinical judgment.

In case of a temporary reason, trial treatment should be restarted as early as possible if medically justified.

Page 32 of 84

Even if the trial treatment is permanently discontinued, the patient remains in the trial and, given his/her agreement, will undergo the procedures for early treatment discontinuation, follow up, and vital status collection as outlined in the Flow Chart and Section 6.2.3.

For all patients, the reason for withdrawal from trial treatment (e.g. adverse events) must be recorded in the CRF. These data will be included in the trial database and reported.

If a patient becomes pregnant during a trial, the study medication needs to be discontinued. The patient will be followed up until birth or otherwise termination of the pregnancy. The data of the patient will be collected and reported in the clinical trial report (CTR) until last patient visit and any events thereafter will be reported in the BI Pharmacovigilance database.

3.3.4.2 Withdrawal of consent to trial participation

Patients may withdraw their consent to trial participation at any time without the need to justify the decision. If a patient wants to withdraw consent, the investigator should be involved in the discussion with the patient and explain the difference between trial treatment discontinuation and withdrawal of consent to trial participation, as well as explain the options for continued follow up after trial treatment discontinuation, please see Section 3.3.4.1 above.

3.3.4.3 Discontinuation of the trial by the sponsor

Boehringer Ingelheim reserves the right to discontinue the trial overall or at a particular trial site at any time for the following reasons:

- 1. Failure to meet expected enrolment goals overall or at a particular trial site.
- 2. Emergence of any efficacy/safety information invalidating the earlier positive benefitrisk-assessment that could significantly affect the continuation of the trial (refer to Section 8.7 for DMC role in this process).
- 3. Violation of GCP, the trial protocol, or the contract impairing the appropriate conduct of the trial.

The investigator / the trial site will be reimbursed for reasonable expenses incurred in case of trial termination (except in case of the third reason).

c22181693-04 Page 33 of 84

4. **TREATMENTS**

4.1 INVESTIGATIONAL TREATMENTS

BI 730357 and Placebo to match BI 730357. The placebo will only be given until the open label period of the extension trial begins.

4.1.1 **Identity of the Investigational Medicinal Products**

Table 4.1.1: 1 Test product 1

Substance:	BI 730357	
Pharmaceutical formulation:	Film-coated tablet	
Source:	Boehringer Ingelheim Pharma GmbH & Co KG	
Unit strength:	25 mg, 50 mg, 100 mg	
Posology	q.d.	
Route of administration:	Per os	

Substance:	Placebo to match BI 730357 (until open label drug supply is dispensed)	
Pharmaceutical formulation:	Film-coated tablet	
Source:	Boehringer Ingelheim Pharma GmbH & Co KG	
Unit strength:	Not applicable	
Posology	q.d.	
Route of administration:	Per os	

4.1.2 Selection of doses in the trial and dose modifications

The dose range for Part 1 of the preceding trial 1407-0030 was selected on the basis of the preclinical data, and on safety data obtained in first-in-human SRD trial 1407.1 and MRD trial 1407-0002, which respectively demonstrated that single BI 730357 dose levels of up to 800 mg q.d. and multiple dose levels of up to 200 mg q.d. were well tolerated.

Page 34 of 84

For patients entering from Part 1 of trial 1407-0030, BI 730357 doses of 25, 50, 100, and 200 mg q.d. or placebo as assigned in the preceding Trial 1407-0030, will be continued for patients in the extension trial 1407-0005 for the initial 12 week double-blind treatment period. At Visit 2/Week 12 patients will be assigned to either the 100 mg or 200 mg BI 730357 (refer to Section 3.1). This change in treatment assignment will be supported by a DMC review of all available safety data from trial 1407-0030; if an unacceptable risk regarding the safety of the 200 mg dose level is reported by the DMC, a plan has been provided within the protocol for an alternative dosing scheme with all patients assigned to the 100 mg BI 730357 open label treatment dose (refer to Section 8.7). Patients currently enrolled at the 100 mg *q.d.* dose at the time Part 2 begins will have the option of increasing to the 200 mg dose based upon investigator assessment that the increased dose could benefit the patient.

Based on PK-PD modeling developed to describe the concentration and PASI data obtained in Part 1 of trial 1407-0030, Part 2 of 1407-0030 extends dose ranging of BI 730357 to 400 mg *q.d.* and 200 mg *b.i.d.*, to be administered under fed conditions. The target human therapeutic efficacy exposures are currently based on 400 mg administered *q.d.* under fed conditions to patients with moderate-to-severe plaque PsO (P20-07441). Therefore, for patients entering from Part 2 of trial 1407-0030, BI 730357 400 mg *q.d.* is to be administered to all eligible patients.

4.1.3 Method of assigning patients to treatment groups

For patients entering from Part 1 of trial 1407-0030, during visit 1, eligible patients will continue to receive their treatment allocation of BI 730357 received in the preceding study, in a blinded fashion, via Interactive Response Technology (IRT). Upon completion of Visit 2/Week 12 the patients in this extension study will be assigned to an open label BI 730357 dose, via IRT (refer to Section 3.1).

Patients entering from Part 2 of trial 1407-0030 will all be assigned to open label BI 730357 400 mg q.d.

4.1.4 Drug assignment and administration of doses for each patient

Study medication will be dispensed at the investigational sites according to the Flow Chart. On days of scheduled patient visits, the study medication will be administered at the study site after the other visit procedures have been performed. On days with no scheduled study visit the patient will take their medication at home.

From the start of the treatment period patients will be instructed to take the trial medication once daily with a glass of water. Patients must take the study medication after at least 6 hours fasting and should not eat for 30 minutes after drug administration.

Patients will receive four tablets per day from Visit 1 until Visit 2. In Table 4.1.4: 1, the medication schedule for each treatment group is listed for continuation of the double-blind 1407-0030 dose regimen until Visit 2/Week 12.

Upon the start of the open label treatment at Visit 2/Week 12, patients will be reassigned (see Section 3.1) via IRT to either the 100 mg treatment group or the 200 mg treatment group until

Page 35 of 84

the End of Trial Visit. If a safety signal is identified by the DMC, an alternative dosing plan will be followed and all patients will be assigned via IRT to the 100 mg treatment group until the End of Trial Visit (see Section 3.1 and Section 8.7).

Placebo tablets will no longer be administered during the open label period.

Table 4.1.4: 1 Study medication dosing guide

	25 mg/placebo tablet	50 mg/placebo tablet	100 mg/placebo tablet
25 mg treatment group	1 active	1 placebo	2 placebo
50 mg treatment group	1 placebo	1 active	2 placebo
100 mg treatment group	1 placebo	1 placebo	1 active
			1 placebo
200 mg treatment group	1 placebo	1 placebo	2 active
400 mg treatment group	0 placebo	0 placebo	4 active
Placebo group	1 placebo	1 placebo	2 placebo

To ensure a dose interval of about 24 hours, the medication should be taken in the morning at approximately the same time every day. If a dose is missed by more than 12 hours, that dose should be skipped and the next dose should be taken as scheduled. No double doses should be taken.

Patients should be instructed not to take their medication on the morning of trial visits as they will be dosed in the clinic.

During the COVID-19 pandemic or other unforeseen situations, physical visits to the sites may need to be restricted to ensure patient's safety. Based on a thorough assessment of the benefits and risks, and consultation with the CTM, the investigator may still decide to continue the trial treatment and trial medication may be shipped to the patient's home if acceptable according to local law and regulations.

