each treatment	of patients that participate in the extension study. Approximate
	possible ranges provided.

Page 3 of 84

Patients entering extension trial from Part 1 of trial 1407-0030 (Fasted) double blind treatment period until Week 12: • 25 mg (0 to 40 patients) • 50 mg (0 to 80 patients) • 100 mg (0 to 80 patients) • 200 mg (40 to 100 patients) • placebo (0 to 20 patients) (Fasted) open label treatment period: • 100 mg (80 to 140 patients) • 200 mg (60 to 100 patients)
Patients entering extension trial from Part 2 of trial 1407-0030
(Fed) open label treatment period:400 mg (0 to 90 patients)
Patients with moderate-to-severe plaque psoriasis who have
completed treatment in the preceding trial
 Have completed treatment in the preceding trial without early discontinuation, agree to continue treatment in 1407-0005, and for patients entering from Part 1 of trial 1407-0030 ≥PASI50 response upon completing the trial 1407-0030 Week 24 end-of-treatment visit for patients entering from Part 2 of trial 1407-0030 ≥PASI50 response upon completing the trial 1407-0030 Week 12 end-of-treatment visit or perceived patient improvement, at the discretion of the Investigator. Women of childbearing potential (WOCBP) must be ready to use highly effective methods of birth control Have not developed any of the exclusion criteria of the preceding trial, including relevant chronic or acute infections Must agree to continue to avoid intake of any restricted medication No plan to receive a live vaccination during trial conduct Must agree to continue to adhere to the rules of UV-light protection No ongoing AEs related to trial medication (including gastric intolerance) from 1407-0030
BI 730357
25 mg, 50 mg, 100 mg, 200 mg, 400 mg BI 730357 per day
Oral (p.o.)

Boehringer Ingelheim BI Trial No.: 1407-0005

c22181693-04

Comparator product(s)	Placebo to BI 730357 (for patients entering from Part 1 of trial
	1407-0030, 12 week double blind period only)
dose	Not applicable
method and route of administration	p.o.
Duration of treatment	Approximately 6 years
Statistical methods	Descriptive statistics include exposure adjusted rate of patients
	reporting a TEAE, responder analysis, and time to loss of response.

Proprietary confidential information © 2020 Boehringer Ingelheim International GmbH or one or more of its affiliated companies

FLOW CHART

Trial Periods	Screening/ Double Blind Treatment							(Open La	abel Tr	eatment	t						

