4.2.2.2 Restrictions on diet and life style

The participants should take the medication after at least 6 hours fasting and should not eat for 30 minutes after drug administration.

Foods which are known strong or moderate inhibitors of CYP 3A (e.g., seville oranges, grapefruit, paw paw and their products) should be avoided during the study participation.

Moisturizers/emollients containing retinoids and the use of tanning beds are not allowed during the study.

Throughout their participation in the study, patients should avoid prolonged exposure to sunlight and artificial UV-light. When exposed to direct sunlight study participants should protect skin areas not covered by clothes by using sun-protection creams and lip balms with sun protection factor 30 or higher with protection against UV-A and UV-B. Patients should wear sunglasses when exposed to direct sun or other sources of UV-light. These protection measures must be applied until the end of the follow-up periods.

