6. GENERAL ANALYSIS DEFINITIONS

6.1 TREATMENT(S)

All patients need to complete the preceding Phase II psoriasis Trial 1407-0030 and meet entry criteria for this study.

Two groups of patients are to be entered into this trial, including up to (approximately) 180 patients entered in the original trial 1407-0030 protocol (now Part 1) and approximately 90 patients entered in an extended dose-ranging segment, now Part 2 of the amended trial 1407-0030 protocol. Actual numbers of subjects entering the extension trial are to be determined by response in the preceding study.

In the first group (Part 1), patients will be considered eligible to participate in this long-term extension trial upon completing the trial 1407-0030 Week 24 end-of-treatment visit with a \geq PASI50 response. BI 730357 dose levels of up to 200 mg *q.d.* are to be administered under fasting conditions to patients in this group, reflecting the dose levels evaluated during Part 1 of trial 1407-0030.

- Patients entering the extension trial will remain on their blinded BI 730357 dose treatment from the preceding trial until the open label period of 1407-0005 begins at Visit 2/Week 12.
- At Visit 2/Week 12, patients presently assigned to double blind treatment of placebo, 25 mg, 50 mg, and 100 mg will be reassigned to the 100 mg open label dose, and patients presently assigned to the double blind treatment of 200 mg will be reassigned to 200 mg open label dose.

In the second patient group (Part 2), patients will be considered eligible to participate in this trial upon completing the trial 1407-0030 Week 12 end-of-treatment visit with a \geq PASI50 response or perceived patient improvement, at the discretion of the Investigator. Patients are to be considered eligible only if also without ongoing AEs consistent with intolerance of trial medication (including gastric intolerance) that in the opinion of the investigator would compromise the safety of the patient.

.

- All patients entering the extension trial are to be assigned at Visit 1 to receive open-label treatment with 400 mg *q.d.* (fed), the anticipated therapeutic BI 730357 dose.

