It is expected that Visit 1 of trial 1407-0005 will be performed on the same day of the EOT Visit of trial 1407-0030 in both patient groups. In the event that patients completing Part 2 of trial 1407-0030 are not able to be entered immediately into the extension trial due to administrative reasons (e.g., pending protocol approval, availability of trial medication), Visit 1 of the extension trial may be delayed for no more than 16 weeks.

The treatment period in this trial will be approximately 6 years.

Figure 6.1: 1

Trial 1407-0005 dose assignment/reassignment for patients entering from Part 1 of trial 1407-0030

[figure not shown]
[figure not shown]

Figure 6.1: 2

Trial 1407-0005 dose assignment for patients entering from Part 2 and continuing from Part 1 of trial 1407-0030

Dose selection at Week 12 is based on the safety and tolerability data from the SRD Trial 1407.1 and the MRD Trial 1407-0002, and will be contingent on DMC evaluation of all available data from Phase II trial 1407-0030. For patients entering from Part 1 of trial 1407-0030, if an unacceptable risk regarding the safety of the 200 mg dose level is reported by the DMC, the open label BI 730357 dose assignments beginning at Week 12, is to be altered to assign all patients to the 100 mg *q.d.* dose group.

All patients entering from Part 2 of trial 1407-0030 are to receive the 400 mg *q.d.* dose, as long as no unacceptable risks are identified during Part 2 of trial 1407-0030. Once Part 2 patients begin enrolling in this trial, existing patients receiving 100 mg *q.d.* in this trial will be given the option to titrate up to the 200 g *q.d.* dose, if the investigator determines that the Patients may benefit from the higher dose.

The first Part 2 patients enrolled in this study on December 10, 2020 and at that time all Part 1 patients had been in the study more than 12 weeks and had titrated to 100 mg *q.d.*

Subjects will be analyzed according to the treatment to which they were treated. The following study periods based on actual start and stop dates of study treatment administration are defined as follow.

Table 6.1: 1 Definition of Treatment Periods

Analysing Treatment Period	Start Date	Stop Date
Screening [#]	NA	NA
On-treatment*	Date/Time of the first administration of trial treatment	Date of the last administration of trial treatment + REP
Follow-up	Date of the last administration of trial treatment + REP+1 day	Date of the last per protocol visit

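### The fasting rule in Protocol 4.1.4 and 4.2.2.2 is not limited to Part 1 and contradicts the fed 400 mg regimen assigned to Part 2

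*Protocol*

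**What the plan says.** The food condition assigned to each part is consistent wherever the regimen is defined.

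- **Synopsis.** Both Part 1 periods are labelled fasted. The Part 2 entry reads "Fed) open label treatment period:400 mg (0 to 90 patients".
- **Protocol 3.1, Part 1.** Doses up to 200 mg "are to be administered under fasting conditions to patients in this group, reflecting the dose levels evaluated during Part 1 of trial 1407-0030".
- **Protocol 3.1, Part 2.** "All patients entering the extension trial are to be assigned at Visit 1 to receive openlabel treatment with 400 mg q.d. (fed").
- **Protocol 4.1.2.** The target exposure is based on 400 mg once daily given "under fed conditions to patients with moderate-to-severe plaque PsO", and this is the stated reason for giving 400 mg to all Part 2 patients.
- **SAP 6.1.** It repeats both conditions and describes the Part 2 regimen as 400 mg once daily ("fed), the anticipated therapeutic BI 730357 dose".

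The sections that say how to take the drug are different.

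- **Protocol 4.1.4.** "Patients must take the study medication after at least 6 hours fasting and should not eat for 30 minutes after drug administration".
- **Protocol 4.2.2.2.** "The participants should take the medication after at least 6 hours fasting and should not eat for 30 minutes after drug administration".

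**The concern.** The two sections that a site would consult for dosing instructions contradict the assigned Part 2 regimen. A site cannot satisfy both: dosing with food breaks a mandatory sentence in 4.1.4, and dosing fasted departs from 3.1.

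The question is live. SAP 6.1 records that "The first Part 2 patients enrolled in this study on December 10, 2020".

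If sites resolve the conflict differently, the 400 mg group would mix fed and fasted dosing. SAP 6.1 reports that group as one adverse event column and one efficacy group, and no readable analysis separates the two conditions. Treatment compliance (Protocol 4.3, SAP 7.3) is based on counts of medication taken, so it would not reveal a dose taken in the wrong food state. Part 1 summaries are not affected.

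**Working it through.** The plan has no figure to reproduce here, so the check is a comparison of text followed by a count of how far the wording reaches.

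**Can 4.1.4 be read as applying to Part 1 only?** The paragraphs after the fasting sentence describe the Part 1 scheme: four tablets a day until Visit 2, then reassignment to 100 mg or 200 mg. The sentence looks like Part 1 text that was left in place. The restricted reading still fails, for four reasons:

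1. The heading of 4.1.4 covers each patient, and its dosing table has a 400 mg row, which only Part 2 receives.
2. The rule is tied to the start of the treatment period and comes before any Part 1 material.
3. Where the protocol means one part it says so, as in 4.1.2, 4.1.3 and 4.1.5.1. Section 4.1.4 has no such qualifier.
4. Section 4.2.2.2 has no Part 1 context at all.

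**Does 6.2.2 add to the conflict?** It requires patients to be fasted at each visit. That alone is compatible with fed dosing, because a patient can arrive fasted, have bloods drawn, eat, and then take the dose. No text describes that meal.

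**Reach of the wording**

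- Part 2 patients: 0 to about 90 (synopsis). Total planned: up to about 270 (Protocol 7.7).
- Share: 0/270 = 0% to 90/270 = 33%.

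**Where the doses are taken, for a Part 2 patient who completes 288 weeks**

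- Scheduled daily doses: 288 × 7 = 2,016.
- Clinic visits with on-site dosing before end of treatment (Flow Chart): Visits 1, 1.1, 1.2 and 1.3 (4), Visit 2 (1) and Visits 3 to 24 (22), so 4 + 1 + 22 = 27. Visit 2.1 does not apply to Part 2.
- Clinic doses: 27/2,016 = 1.3%.
- Home doses: 2,016 − 27 = 1,989, and 1,989/2,016 = 98.7%.

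This count assumes that every visit takes place on site. Remote visits would raise the home share slightly. It shows where an instruction acts and does not measure error.

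**The case against.** The strongest reply is that misdosing is unlikely. The fed regimen is stated in several places. Protocol 3.2 says Part 2 of 1407-0030 was itself dosed with food, so these patients arrive used to fed dosing, normally with Visit 1 on the same day as their last visit in that trial. Within 4.1.4, unqualified references to patients elsewhere plainly mean Part 1; read literally, they would also move Part 2 patients off 400 mg at Week 12, which nobody intends. Home instructions reach patients through the patient information, labels and site file, which are not among the documents and may be correct. The trial is descriptive, with no hypothesis tests.

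Much of this stands. No divergence between sites is shown, and neither the size nor the direction of any change in exposure can be stated. The problem is better described as an inconsistency between sections than as a poor choice of design.

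The contradiction remains. Prior fed dosing does not help if the extension's own mandatory sentence tells the site to change it. The argument from context in 4.1.4 meets the 400 mg table row and does not touch 4.2.2.2. A descriptive trial still needs its single 400 mg group to represent one regimen.

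**Conclusion.** The concern holds. The protocol states a mandatory daily dosing rule that, if followed, gives Part 2 patients a regimen other than the one assigned and used as the basis for the dose. This is a wrong instruction, not missing detail, and it must be corrected.

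Up to a third of planned patients fall within the wording, for up to 288 weeks each. That figure assumes Part 2 fills to its planned maximum, and it does not estimate how many patients were dosed fasted. Confidence is high that the texts conflict. The conclusion makes no claim about the effect on the 400 mg results.

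**What to change.** 1. In Protocol 4.1.4 and 4.2.2.2, limit the fasting sentences to patients who come from Part 1 of 1407-0030, and add that patients who come from Part 2 take 400 mg once daily with food. State what counts as fed (type of meal and its timing relative to the dose), so that the instruction is not left to each site.
2. In Protocol 6.2.2, add that on visit days Part 2 patients arrive fasted, complete bloods and assessments, and then eat before the on-site dose.
3. Write to sites with the corrected instruction, and ask whether any Part 2 patient has been dosed fasted and for how long. If so, record it and describe those patients alongside the 400 mg summaries.

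The cost is a few sentences of protocol wording and a site letter. The wording change goes through the approval that Protocol 8.1 requires for amendments, and the 6.2.2 addition means a meal on site at up to 27 visits per completing Part 2 patient. No new assessments or patients are needed.
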